4.2.3.2 Derivations

Change from baseline in post-BD FEV1 to Weeks 4, 12 and 24 will be calculated as specified in Section 3.3.1.2.

4.2.3.3 Handling of Dropouts

The 'while-on treatment' strategy will be used: which means that if an intercurrent event occurs all subsequent data for that participant are excluded from the evaluation.

4.2.3.4 Primary Analysis of Secondary Endpoint

Observed values and absolute change from baseline up to Weeks 4, 12 and 24 in post-BD FEV1 will be summarised by each intervention group for the FAS population.

Change from baseline to Week 4, Week 12 and Week 24 in post-BD FEV1 for participants with moderate to severe COPD will be analysed using MMRM as described in Section 3.4.3.

The analysis will be focused on the FAS population.

4.2.3.5 Sensitivity Analyses of the Secondary Endpoint

Not applicable.

4.2.3.6 Supplementary Analyses of the Secondary Endpoint

The analysis described above (Section 4.2.3.4) will be repeated applying the "treatment policy" estimand strategy as supportive. This means if an intercurrent event occurs all subsequent data for that participant up to last dose are included in the evaluation.

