To evaluate the effect of mitiperstat (AZD4831) as compared to placebo on the time to first COPDCompEx event in patients with moderate to severe COPD.	Population: all participants randomised to either active or placebo arm. Endpoint: time to first COPDCompEx event. Population level-summary measure: hazard ratio. Strategy for intercurrent events: Primary estimand: while on treatment – if an intercurrent event occurs before first COPDCompEx event, the participant will be censored at the time of intercurrent event. Supportive estimand: treatment policy (reflects ITT principle) – after intercurrent event participants remain in the study so that the endpoint can be observed. Treatment policy strategy used to estimate the efficacy of mitiperstat (AZD4831) in 'real-world' conditions.
6 1	conditions.
Secondary	
To assess the PK of mitiperstat (AZD4831) in patients with moderate to severe COPD.	Population: all participants who had received at least one dose of mitiperstat (AZD4831), and who had at least one measurable PK sample post dose. Endpoint: plasma mitiperstat (AZD4831) concentration-time profiles during the intervention and follow-up periods, and PK parameters. Population level-summary measure: summary statistics. Strategy for intercurrent events: while on treatment.
To evaluate the effect of mitiperstat (AZD4831)	Population: all participants randomised to either
as compared to placebo on the time to first moderate or severe COPD exacerbation.	active or placebo arms. Endpoint: time to first COPD exacerbation event ^b
	Population level-summary measure: hazard ratio.
	Strategy for intercurrent events: while on

Objectives	Estimand Description ^a				
	treatment.				
To assess the effects of mitiperstat (AZD4831) as compared to placebo on post-BD FEV1 in	Population: all participants randomised to either active or placebo arms.				
patients with moderate to severe COPD.	Endpoint: change from baseline in post-BD FEV1 after 12 weeks.				
	Population level-summary measure: the				
	difference in mean.				
	Primary estimand: while on treatment.				
	Supportive estimand: treatment policy.				
To assess the effect of mitiperstat (AZD4831) compared with placebo on respiratory	Population: all participants randomised to either active or placebo arms.				
symptoms in patients with moderate to severe COPD.	Endpoint: change from baseline in EXACT, BCSS score, and Cough VAS at Week 12 and Week 24				
	Population level-summary measure: the difference in mean.				

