3 OBJECTIVES AND ENDPOINTS

Table 3Objectives and Endpoints

Objectives	Estimand description ^a
Primary	
To evaluate the effect of mitiperstat (AZD4831) as compared to placebo on the time to first COPDCompEx event in patients with moderate to severe COPD.	Population: all participants randomised to either active or placebo arm. Endpoint: time to first COPDCompEx event. Population level-summary measure: hazard ratio. Strategy for intercurrent events: Primary estimand: while on treatment – if an intercurrent event occurs before first COPDCompEx event, the participant will be censored at the time of intercurrent event. Supportive estimand: treatment policy (reflects ITT principle) – after intercurrent event participants remain in the study so that the and point can be observed. Treatment policy.
	endpoint can be observed. Treatment policy strategy used to estimate the efficacy of mitiperstat (AZD4831) in 'real-world' conditions.
Secondary	
To assess the PK of mitiperstat (AZD4831) in patients with moderate to severe COPD.	Population: all participants who had received at least one dose of mitiperstat (AZD4831), and who had at least one measurable PK sample post dose. Endpoint: plasma mitiperstat (AZD4831) concentration-time profiles during the intervention and follow-up periods, and PK parameters. Population level-summary measure: summary statistics. Strategy for intercurrent events: while on
	treatment.
To evaluate the effect of mitiperstat (AZD4831) as compared to placebo on the time to first moderate or severe COPD exacerbation.	Population: all participants randomised to either active or placebo arms. Endpoint: time to first COPD exacerbation event ^b Population level-summary measure: hazard ratio. Strategy for intercurrent events: while on

Table 3Objectives and Endpoints

Objectives	Estimand description ^a
To assess the effects of mitiperstat (AZD4831) as compared to placebo on post-BD FEV1 in patients with moderate to severe COPD.	Population: all participants randomised to either active or placebo arms. Endpoint: change from baseline in post-BD FEV1 after 12 weeks.
	Population level-summary measure: the difference in mean. Primary estimand: while on treatment. Supportive estimand: treatment policy.

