3.4.3 Mixed Model Repeated Measures (MMRM)

The MMRM model will be used to fit change from baseline for continuous endpoints that have data at several post-baseline visits. The model will include all available data from all visits, irrespective of whether the patient discontinued study intervention. Since a repeated measures model is being applied, no imputation will be made for missing data. Region will be added as a random effect. The model will include fixed effects for baseline, visit, study intervention and the baseline by visit and study intervention by visit interactions. An unstructured covariance matrix will be used to describe the correlations on a patient between visits, and the Kenward-Roger correction will be used for degree of freedom approximation in the generation of the model. In the event that the model with unstructured covariance matrix fails to converge, an alternative such as autoregressive or compound symmetry will be used instead. Estimates of the least square (LS) mean change from baseline for each study intervention, and the difference between them (AZD4831-placebo), together with two-sided 90% CI, will be obtained from the model for each visit. The study intervention effect will be tested at the 10% two-sided level of significance.

The reportable results from the model are:

- The LSmeans change from baseline at each visit and their standard errors for each study intervention group.
- The difference in change from baseline at each visit between AZD4831 and placebo (LSmeans difference) together with its two-sided 90% confidence interval (CI).
- The two-sided p-value for the difference in change from baseline at each visit between AZD4831 and placebo.

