To investigate whether cough frequency is associated with lung function (eg, PEF, FEV1), cough/COPD symptom scores (eg, BCSS, CAT and Cough VAS) and blood biomarkers (eg, MPO concentration).	Average cough frequency measured over a 24-hour period as measured at start of treatment (Visit SV3) and after 12 weeks treatment (Visit SV5) using the VitaloJAK Cough® Monitor device.	Cough subset
To assess the effects of AZD4831 as compared to placebo on COPDCompEx in participants with moderate to severe COPD.	Annualised rate of COPDCompEx events, based on the period from baseline to the last dose Strategy for intercurrent events: while on treatment.	FAS
To assess the effect of AZD4831 compared with placebo on moderate to severe COPD exacerbation.	Annualised rate of moderate or severe COPD exacerbations based on the period during the intervention from baseline to the last dose Strategy for intercurrent events: while on treatment.	FAS

COPD Exacerbation: a worsening in the participant's usual COPD symptoms that is beyond normal day-to-day variation, is acute in onset, lasts 2 or more days (or less if the worsening is so rapid and profound that the treating physician judges that intensification of treatment cannot be delayed), may warrant a change in regular medication, and leads to any of the following:

- Use of systemic corticosteroids for at least 3 days; a single depot injectable dose of corticosteroids will be considered equivalent to a 3-day course of systemic corticosteroids.
- Use of antibiotics to treat COPD exacerbation for at least 3 days.
- An inpatient hospitalisation due to COPD (defined as an inpatient admission ≥ 24 hours in the hospital, an observation area, the emergency department, or other equivalent healthcare facility depending on the country and healthcare system).
- Admission in emergency department or emergency room due to COPD for < 24 hours requiring intensive treatment.
- Results in death.

Intercurrent events are events occurring after treatment initiation (eg, premature treatment discontinuation, switching treatment, terminal events such as death) that affect either the measurement or interpretation of the summary measure (eg, hazard ratio) associated with the clinical question of interest. This study contains 2 intercurrent events:

- 1 Premature treatment discontinuation (with the following reasons: SAE, death not due to exacerbation, COVID-19, pneumonia, other).
- 2 Prohibited medication.

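### The supportive treatment-policy analysis of post-bronchodilator FEV1 is cut at last dose, so for permanent discontinuation it repeats the while-on-treatment analysis

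*SAP*

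**What the plan says.** Protocol Section 3 (Table 3) sets the FEV1 estimands as "Primary estimand: while on treatment. Supportive estimand: treatment policy", with no limit at last dose. The protocol explains treatment policy only in the primary-endpoint row, where "after intercurrent event participants remain in the study so that the endpoint can be observed".

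The SAP lists two intercurrent events. One is prohibited medication; the other is "Premature treatment discontinuation (with the following reasons: SAE, death not due to exacerbation, COVID-19, pneumonia, other").

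For FEV1 the SAP then says:

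- **4.2.3.3, while on treatment:** "if an intercurrent event occurs all subsequent data for that participant are excluded from the evaluation".
- **4.2.3.4, primary analysis:** the change from baseline "will be analysed using MMRM as described in Section 3.4.3".
- **4.2.3.5, sensitivity analyses:** "Not applicable".
- **4.2.3.6, treatment policy:** the analysis is repeated, and after an intercurrent event "all subsequent data for that participant up to last dose are included in the evaluation".

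The shared model text in 3.4.3 reads: "The model will include all available data from all visits, irrespective of whether the patient discontinued study intervention".

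SAP Section 2, which lists departures from the protocol analyses, includes a change to the handling of baseline spirometry but not a last-dose cut for treatment policy.

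**The concern.** A treatment-policy run is there to show whether the FEV1 result depends on removing data collected after drug is stopped. To do that it must contain such data. With the cut at last dose it contains none for participants who stop permanently, although the protocol arranges for one value to be collected: the Schedule of Activities and Protocol 8.2.3 place face-to-face spirometry at SV7/EDV.

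The report would then show two FEV1 tables under different estimand labels. A reader would take their agreement as evidence of robustness when, for discontinuation, it follows from the definition. No other FEV1 sensitivity or supplementary analysis in SAP 4.2.3 would reveal this.

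The SAP is also inconsistent. The mixed-model text keeps data after discontinuation, which contradicts 4.2.3.6 and equally contradicts the while-on-treatment rule in 4.2.3.3. Two programmers could produce different tables from the same plan.

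**Working it through.** **Comparison of record sets.** The plan gives no figure to reproduce; the point is one of logic.

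1. While on treatment (4.2.3.3) keeps FEV1 records dated on or before the intercurrent event.
2. Treatment policy as written (4.2.3.6) keeps records dated on or before last dose.
3. If the event is a permanent stop dated at last dose, the two conditions are the same.

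I checked this over last dose on Days 1 to 164 and an EDV 0 to 21 days later, which is 164 × 22 = 3608 patterns, with clinic spirometry at Days 28 and 84 while on drug and at the EDV.

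| Date given to the event | Sets identical | Treatment policy has more | Treatment policy has fewer |
|---|---|---|---|
| Last dose | 3608 | 0 | 0 |
| Last dose + 1 day | 3444 | 0 | 164 |
| Last dose + 5 days | 2788 | 0 | 820 |

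The SAP does not define the event date, but no choice gives the supportive run an extra record. Without the cut it would gain the EDV record in 3444 patterns, that is, all except the 164 with the EDV on the last-dose day. These counts show the logic; they are not expected frequencies.

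**How many participants could be affected.** The documents give no discontinuation rate, timing of stops or EDV delay, so all three are assumed.

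Inputs from the documents: 406 randomised; SAP Table 3 windows for clinic spirometry (Week 4 to Day 56, Week 12 from Day 57 to 127); closest assessment to the scheduled day used (SAP 3.3.3); SV4 on Day 28; SV5 on Day 84.

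Let a proportion p stop before Week 12 at a constant rate, so the proportion still on drug after day t is S(t) = (1 − p)^(t/84). With the EDV L days after last dose, it is the only Week 12 value when last dose falls on Days 57 − L to 83:

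n = 406 × [S(56 − L) − S(83)]

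Example with p = 10%, L = 1: 406 × (0.93334 − 0.90113) = 13.1.

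| Stop before Week 12 | L = 1 day | L = 3 days | L = 7 days |
|---|---|---|---|
| 5% | 6.7 | 7.1 | 8.1 |
| 10% | 13.1 | 14.0 | 15.9 |
| 20% | 25.1 | 27.0 | 30.8 |

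The range is 7/406 = 1.7% to 31/406 = 7.6%.

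At L = 3 the other stops divide as follows. The EDV becomes the Week 4 value for 6.6, 13.5 or 28.1 participants, and is unused because SV4 is closer to Day 28 for 6.3, 12.6 or 25.2.

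**Early stops.** Protocol 4.3 reports rash around 7 to 10 days after first dose in healthy subjects, and Protocol 7.1 requires a permanent stop for maculopapular rash. If half of the stops fall on Days 7 to 14 (an assumed share), those EDVs fall in the Week 4 window and the Week 12 counts halve: 3 to 4, 7 to 8, or 13 to 15.

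**Same-day EDV.** With L = 0 the EDV is kept in both runs and the count is 0. Protocol 7.2 makes this possible at study withdrawal.

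**The case against.** Five arguments deserve an answer.

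- **Discontinuation need not mean a permanent stop.** Neither intercurrent-event list uses that word, and COVID-19 and pneumonia lead first to temporary interruption under Protocol 7.1.2. If interruptions counted as events, the runs could differ for them. However, SAP 4.1.1.1 ties treatment discontinuation to a permanent stop, and the concern is limited to that case.
- **General rules may override the cut.** SAP 3.4.3 keeps all data, 3.3.4 brings early discontinuation visits into the windows, and 4.2 runs endpoint analyses to the end-of-treatment visit. These are general rules, while 4.2.3.6 defines the strategy for this endpoint. At best the SAP contradicts itself, which still needs resolving.
- **Another FEV1 analysis may already do the job.** SAP 4.2.9 analyses face-to-face spirometry, including FEV1, under treatment policy with no last-dose limit stated. It does not define the strategy either, so it is unclear whether Tables 14.2.2.11 and 14.2.4.4 use the same FEV1 data.
- **Extending the fix to cough frequency and sputum MPO adds little.** This stands: neither is scheduled at the EDV, so aligning those sections is for consistency.
- **The effect is small.** This is a supportive run of a secondary endpoint with no formal sample size, in a Phase IIa trial, and the counts rest on assumptions. That limits the size of the point but leaves the rule wrong as written. The 1 to 7 day delay also omits one route: Protocol 7.1.2 withdraws participants from study drug after 28 or more continuous days without it, which puts the EDV at least 28 days after last dose.

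**Conclusion.** The concern holds. For permanent discontinuation, the FEV1 analysis labelled treatment policy cannot contain any record that the while-on-treatment analysis lacks. It departs from the protocol's supportive estimand, the departure is not listed in SAP Section 2, and it conflicts with the model text that both runs use.

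The two analyses are not identical overall, because they can still differ for prohibited medication taken before last dose. Under the assumed rates and EDV delays, correcting the rule would give about 7 to 31 of 406 participants a Week 12 value, roughly half that if stops cluster early, and none if every EDV is on the last-dose day. Additional Week 24 values are not counted. The effect on the estimated treatment difference cannot be calculated, because the documents give no FEV1 standard deviation, effect size or discontinuation rate.

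Even when corrected, this would be a limited check: SV8 has no spirometry, so each participant who stops contributes at most one value after stopping. The change should be made, but the trial's main conclusion does not depend on it.

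**What to change.** - **SAP 4.2.3.6:** replace the last-dose limit with data up to and including SV7/EDV, regardless of the date of last dose.
- **SAP 4.2.9.3:** state the same definition, so that the two FEV1 tables can be compared.
- **SAP 4.2.8.3 and 4.3.1.2:** use the same definition for cough frequency and sputum MPO, or say why it differs.
- **SAP 3.4.3:** restrict the sentence on including data irrespective of discontinuation to the treatment-policy runs.
- **If the cut at last dose is intended:** list it in SAP Section 2 and do not label the run treatment policy.

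The cost is SAP wording only. The EDV spirometry is already scheduled and already assigned to analysis windows, so no protocol amendment or new data are needed.

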4.2.3.7 Subgroup Analyses

The subgroup analysis will be conducted for exploratory purposes.

For subgroup categories that contain at least 20% of the total participants a single forest plot including all subgroups will display graphically the mean difference (AZD4831 - Placebo) in change from baseline in post-BD FEV1 at Week 12, together with the two-sided 90% CI and reference line at zero. In addition, the following statistical parameters will be displayed: total number of subjects, mean change from baseline and its standard error for each study intervention, as well as the mean difference (AZD4831 - Placebo) from baseline, together with the two-sided 90% CI.

For subgroup categories that contain less than 20% of the total participants, only the total number of subjects in each arm will be presented.

Following are the subgroups:

- Frequent Productive Cough (Yes; No)
- Gender (Male; Female)
- Age $(\ge 40 < 65; \ge 65 \le 80)$
- Race (as collected in CRF)
- BMI (<18; ≥ 18 to <25; ≥ 25 to <30; ≥ 30)
- Geographic region (North America (Canada, United States of America), Eastern Europe (Bulgaria, Poland, Turkey), Western Europe (Denmark, Germany, Italy, Netherlands, Spain, United Kingdom), Rest of the world (Argentina, Mexico, South Africa))
- Baseline FEV1 as percent of predicted (<50%; ≥50%)
- Maintenance medications:

- o ICS; no ICS
- LABA/ICS; LABA/LAMA/ICS; LABA/LAMA
- Number of COPD exacerbations in last 24 months ($\langle 2; \geq 2 \rangle$)
- Type of site of recruitment (primary care site; specialist care site)
- Smoking status (Current smokers; Ex-smokers)
- MPO concentration at baseline (upper tertile; middle tertile; lower tertile)

4.2.4 Secondary Endpoint – EXACT score

4.2.4.1 Definition

The exacerbations of chronic pulmonary disease tool (EXACT) is a PRO measure designed to standardize the method for evaluating the frequency, severity, and duration of both reported and unreported acute exacerbations of COPD and chronic bronchitis in clinical trials.

The EXACT total score is computed across 14 items and has a theoretical range of 0 to 100, with higher values indicating a more severe condition. Additional information regarding the patient's condition can be obtained through 3 domain scores embedded in the measure: Breathlessness, Cough & Sputum, and Chest Symptoms. These scores also range from 0 to 100, with higher scores indicating more severe symptoms. The EXACT will be performed at on-site visits using the e-Diary.

4.2.4.2 Derivations

The derivation of the EXACT total and 3 domain scores can be found in EXACT user manual v8.0. Change from baseline in EXACT total and domains scores to Weeks 12 and 24 will be calculated as specified in Section 3.3.1.2.

4.2.4.3 Handling of Dropouts

The 'while-on treatment' strategy will be used: which means that if an intercurrent event occurs all subsequent data for that participant are excluded from the evaluation.

4.2.4.4 Primary Analysis of Secondary Endpoint

Observed values and absolute change from baseline up to Weeks 12 and 24 in EXACT total and domain scores will be summarised by each intervention group for the FAS population.

Change from baseline to Weeks 12 and 24 in EXACT (total and domain scores) will be analysed using MMRM as described in Section 3.4.3.

LSMean change from baseline and two-sided 90% CI up to Weeks 12 and 24 in EXACT total and domain scores will be presented in figures. For primary analysis, LSMean change from baseline through Weeks 12 and 24 in EXACT total and domain scores will be presented.

A listing including results from each of the domain and the total EXACT score will be produced for the FAS population.

4.2.4.5 Sensitivity Analyses of the Secondary Endpoint

Not applicable

4.2.4.6 Supplementary Analyses of the Secondary Endpoint

Not applicable

4.2.4.7 Subgroup Analyses

Not Applicable

4.2.5 Secondary Endpoint – BCSS score

4.2.5.1 Definition

Breathlessness, Cough and Sputum Scale (BCSS) is a 3-item questionnaire rating breathlessness, sputum, and cough on a 5-point Likert scale from 0 (no symptoms) to 4 (severe symptoms). Item scores can be reported as domains scores and are summed to yield a total score. The BCSS will be captured each evening via the e-Diary. If there are repeated measurements in a day (evening), then the first measurement will be used in the analysis.

4.2.5.2 **Derivations**

Change from baseline in BCSS average score to Weeks 12 and 24 will be calculated as specified in Section 3.3.1.2.

4.2.5.3 Handling of Dropouts

The 'while-on treatment' strategy will be used: which means that if an intercurrent event occurs all subsequent data for that participant are excluded from the evaluation.

4.2.5.4 Primary Analysis of Secondary Endpoint

Observed values and absolute change from baseline to Weeks 12 and 24 in BCSS average total and domain scores will be summarised by each intervention group for the FAS population.

Change from baseline to Weeks 12 and 24 in BCSS average total and domain scores will be analysed using MMRM as described in Section 3.4.3.

LSMean change from baseline and two-sided 90% CI up to Weeks 12 and 24 in BCSS average total and domain scores will be presented in figures. For primary analysis, LSMean

change from baseline through Weeks 12 and 24 in BCSS average domain and total scores will be presented.

A listing including results from each of the domain and the total BCSS average score will be produced for the FAS population.

